6.2. Study Objectives

Primary Objectives

The co-primary objectives of this study are to (using screening CS with histopathology as the reference method):

- Estimate the sensitivity for CRC (Sn_{CRC})

This document contains confidential, proprietary information and may not be reproduced or disclosed in whole or in part without written authorization from Freenome Holdings, Inc

		Approval Status	Approved
		Effective Date	5-Jan-2024
Document Number	PL-00052	Current Revision	5
Document Title	Clinical Validation of Freenome's Methylation Blood Test for the Early Detection...		
Document Category	Plan		

- Estimate the specificity for subjects with no evidence of advanced colorectal neoplasia ($Sp_{non-ACN}$)
- Estimate the NPV of the FMBT-CRC for the detection of non-ACN subjects among those with negative FMBT-CRC results ($NPV_{non-ACN}$).
- Estimate the PPV of the FMBT-CRC for the detection of ACN subjects among those with positive FMBT-CRC results (PPV_{ACN})

CI endpoints for all primary objectives must be met to declare the study a success.

Secondary Objective

The secondary objective will be evaluated individually, only if the co-primary objectives have been met.

- Estimate the sensitivity of the FMBT-CRC for AA (Sn_{AA})

6.3. Study Acceptance Criteria

Primary-Objective Acceptance Criteria

The primary objective of this study is to determine that FMBT-CRC is suitable for clinical use. The primary objective will be evaluated using co-primary endpoints of Sn_{CRC} , $Sp_{non-ACN}$, $NPV_{non-ACN}$, and PPV_{ACN} computed from the FAS data.

Acceptance criterion for CRC sensitivity

- the lower bound of the 95% confidence interval for CRC sensitivity, calculated with Wilson's method, shall be greater than 65.0%

Acceptance criterion for non-ACN specificity

- the lower bound of the 95% confidence interval for non-ACN specificity, calculated with Wilson's method, shall be greater than 85.0%

Acceptance criterion for non-ACN NPV

- the lower bound of the 95% confidence interval for $NPV_{non-ACN} - Prevalence_{non-ACN}$ shall be greater than 0.16%, where $NPV_{non-ACN}$ is calculated with NLR and the observed prevalence (FDA, 2017)

This document contains confidential, proprietary information and may not be reproduced or disclosed in whole or in part without written authorization from Freenome Holdings, Inc

		Approval Status	Approved
		Effective Date	5-Jan-2024
Document Number	PL-00052	Current Revision	5
Document Title	Clinical Validation of Freenome's Methylation Blood Test for the Early Detection...		
Document Category	Plan		

Acceptance criterion for ACN PPV

- the lower bound of the 95% confidence interval for PPV_{ACN} – $Prevalence_{ACN}$ shall be greater than 1.17%, where PPV_{ACN} is calculated with PLR and the observed prevalence (FDA 2017)

For the study to be a success, the acceptance criteria for Sn_{CRC} , $Sp_{non-ACN}$, $NPV_{non-ACN}$ and PPV_{ACN} must all be met.

Secondary-Objective Acceptance criterion

The secondary objective will be evaluated only if all the primary objectives are met. The acceptance criteria must be met to declare the success of the secondary objective.

- The lower bound of the 95% confidence interval for AA sensitivity calculated with Wilson's method shall be greater than 11.5%

6.4. Study Endpoints

Primary Endpoints

Sensitivity of FMBT-CRC for CRC

The co-primary endpoint for CRC sensitivity is a two-sided 95% CI based on Sn_{CRC} . The CI will be constructed using the Wilson score method and all FAS subjects identified as CRC by CS and best available evidence, including central histopathology. A lower CI bound that exceeds 65.0% corresponds to rejecting the null hypothesis at the one-sided $\alpha = 0.025$ level.

Specificity of FMBT-CRC for non-ACN

The co-primary endpoint for non-ACN specificity is a two-sided 95% CI based on $Sp_{non-ACN}$. The CI will be constructed using the Wilson score method and all FAS subjects identified as non-ACN by CS and best available evidence, including central histopathology. A lower CI bound that exceeds 85.0% corresponds to rejecting the null hypothesis at the one-sided $\alpha = 0.025$ level.

Negative predictive value of FMBT-CRC for non-ACN

This document contains confidential, proprietary information and may not be reproduced or disclosed in whole or in part without written authorization from Freenome Holdings, Inc

		Approval Status	Approved
		Effective Date	5-Jan-2024
Document Number	PL-00052	Current Revision	5
Document Title	Clinical Validation of Freenome's Methylation Blood Test for the Early Detection...		
Document Category	Plan		

The co-primary endpoint for non-ACN NPV is a two-sided 95% CI based on $NPV_{non-ACN} - Prevalence_{non-ACN}$. The CI will be constructed using NLR and the observed non-ACN prevalence (FDA, 2017), all FAS subjects with a negative FMBT-CRC result, and disease status from CS and best available evidence, including central histopathology. A lower CI bound that exceeds 0.16% among FAS subjects corresponds to rejecting the null hypothesis at the one-sided $\alpha = 0.025$ level.

Positive predictive value of FMBT-CRC for ACN

The co-primary endpoint for ACN PPV is a two-sided 95% CI based on $PPV_{ACN} - Prevalence_{ACN}$. The CI will be constructed using the PLR and observed ACN prevalence (FDA, 2017), all FAS subjects with a positive FMBT-CRC result, and disease status from CS and best available evidence, including central histopathology. A lower CI bound that exceeds 1.17% among FAS subjects corresponds to rejecting the null hypothesis at the one-sided $\alpha = 0.025$ level.

Secondary Endpoint

Sensitivity of FMBT-CRC for AA

The secondary endpoint for AA sensitivity is a two-sided 95% CI based on the observed sensitivity point estimate (Sn_{AA}). The CI will be constructed using the Wilson score method and all FAS subjects identified as AA by CS and best available evidence, including central histopathology. A lower CI bound that exceeds 11.5% corresponds to rejecting the null hypothesis at the one-sided $\alpha = 0.025$ level.

7. Sample Size Justification

The study should include a minimum of 56 evaluable CRC cases meeting the requirements for inclusion in the FAS analysis set for the primary sensitivity endpoint. Assuming a prevalence of 0.30% CRC cases, the minimum number required in the FAS is $56/0.30\% = 19,000$ subjects. Allowing for a 20% unevaluable rate, this gives a required enrollment of 24,000 subjects.

All of the sample size calculations assume the following:

- Power = 90%
- $\alpha = 0.025$

This document contains confidential, proprietary information and may not be reproduced or disclosed in whole or in part without written authorization from Freenome Holdings, Inc

		Approval Status	Approved
		Effective Date	5-Jan-2024
Document Number	PL-00052	Current Revision	5
Document Title	Clinical Validation of Freenome's Methylation Blood Test for the Early Detection...		
Document Category	Plan		

- One-tailed test for greater than the lower bound.
- Statistical power for Specificity_{non-ACN}, Sensitivity_{AA} and Sensitivity_{CRC} were conservatively estimated assuming an exact-binomial distribution, which has greater coverage than Wilson score. Sample size was set such that 90% power was consistently achieved (Chernick 2012).
- The critical value for a given sample size was determined using the Wilson score method.
- From a meta-analysis, the prevalence of CRC is estimated to follow a beta distribution with parameters 3.264 and 816.77; the prevalence of AA is estimated to follow a beta distribution with parameters 34.265, 436.699.
- Given the critical values for Sp_{non-ACN}, Sn_{AA}, and Sn_{CRC}, in addition to the prevalence of AA, CRC, and non-ACN and estimated study size, a distribution of NPV_{non-ACN} and PPV_{ACN} were generated, from which the 2.5th percentile was used for the acceptance criteria.

7.1. CRC Sensitivity Sample Size Justification

Assumption: Sn_{CRC}≥85.0%, a sample size of 56 CRC achieves at least 90% power to reject the hypothesis of true CRC sensitivity of ≤ 65.0%.

If 56 CRC subjects are tested, then at least 44 need to be positive by the FMBT-CRC to reject H₀. The CI lower bound corresponding to 44/56 is 66.2%.

7.2. Non-ACN Specificity Sample Size Justification

Assumption: Sp_{non-ACN} ≥ 90.2%, a sample size of 454 achieves at least 90% power to reject the hypothesis of true non-ACN specificity of ≤ 85.0%.

If 454 non-ACN subjects are tested, then at least 401 need to be negative by the FMBT-CRC to reject H₀. The CI lower bound corresponding to 401/454 is 85.0%.

This document contains confidential, proprietary information and may not be reproduced or disclosed in whole or in part without written authorization from Freenome Holdings, Inc

		Approval Status	Approved
		Effective Date	5-Jan-2024
Document Number	PL-00052	Current Revision	5
Document Title	Clinical Validation of Freenome's Methylation Blood Test for the Early Detection...		
Document Category	Plan		

7.3. Non-ACN Negative Predictive Value Sample Size Justification

Assumption: $NPV_{non-ACN} - \text{Prevalence}_{non-ACN} \geq 0.16\%$.

Given the critical values for $Sp_{non-ACN}$, Sn_{AA} , and Sn_{CRC} , in addition to the prevalence of non-ACN, AA, CRC, and estimated study size, a distribution of $NPV_{non-ACN}$ was generated, from which the 2.5th percentile was used for the acceptance criterion. Since sample size criteria will be met for those other endpoints, additional justification for sample size is not needed.

7.4. ACN Positive Predictive Value Sample Size Justification

Assumption: $PPV_{ACN} - \text{Prevalence}_{ACN} \geq 1.17\%$.

Given the critical values for $Sp_{non-ACN}$, Sn_{AA} , and Sn_{CRC} , in addition to the prevalence of non-ACN, AA, CRC, and estimated study size, a distribution of PPV_{ACN} was generated, from which the 2.5th percentile was used for the acceptance criterion. Since sample size criteria will be met for other endpoints, additional justification for sample size is not needed.

7.5. AA Sensitivity Sample Size Justification

Assumptions: $Sn_{AA} \geq 14.0\%$, a sample size of 1,929 AAs achieves at least 90% power to reject the hypothesis of true AA sensitivity of $\leq 11.5\%$.

If 1,929 AA subjects are tested, then at least 250 need to be positive by FMBT-CRC to reject H_0 . The CI lower bound corresponding to 250/1,929 is 11.53%.

8. Statistical Methods

8.1. General Considerations Impacting the Data Analysis

- The Freenome testing results will be tabulated and data analysis will be performed on the compiled results as described in the study (and data unblinding) protocol.
- Categorical variables will be summarized by presenting the number and percent of observations in each category and the two-sided Wilson score 95% CI, unless otherwise

This document contains confidential, proprietary information and may not be reproduced or disclosed in whole or in part without written authorization from Freenome Holdings, Inc

		Approval Status	Approved
		Effective Date	5-Jan-2024
Document Number	PL-00052	Current Revision	5
Document Title	Clinical Validation of Freenome's Methylation Blood Test for the Early Detection...		
Document Category	Plan		

noted. When calculating percentages, the denominator will be the number of participants in the FAS, unless otherwise specified in the output.

- Continuous variables will be summarized using n (sample size), mean, standard deviation, median, percentiles (25, 50, and 75), minimum and maximum values, and 95% CI for the mean, unless otherwise noted.
- For the statistical analyses, the FMBT-CRC result will be coded as a binary categorical variable.
- Baseline information distributions will be tabulated separately for CRC, AA, ACN, non-ACN, NAA and NEG subjects.

8.2. P values and Confidence Intervals

For primary and secondary endpoints, the one-sided lower 97.5% confidence interval must exceed its respective acceptance criterion. For informational purposes, a p-value may be generated, corresponding to a one-sided test with a significance level of $\alpha = 0.025$. In all other cases, unless otherwise specified, tests will use a nominal 0.05 level of significance, and 95% two-sided CIs will be presented for endpoints based on methods described in Section 6.2

Since all primary endpoints must be met for the primary objective to be achieved, no multiplicity correction is required.

Multiplicity is controlled for the secondary objective because the primary objectives are tested first, and the secondary objective is tested only if all primary objective success criteria are met.

8.3. Baseline Subject Characteristics

Subject demographics will be presented for the ALL, EN, FAS and SAS study populations. This will include the subject's age in years as a continuous variable, age stratified by ranges of clinical interest, biological sex, race and ethnicity, BMI, and lifestyle information (e.g. smoking history and alcohol use).

The age brackets (inclusive of both endpoints) of clinical interest that will be presented are [45 to 49], [50 to 54], [55 to 64], [65 to 74], [75 and greater], and separately, [45 to 54].

This document contains confidential, proprietary information and may not be reproduced or disclosed in whole or in part without written authorization from Freenome Holdings, Inc

		Approval Status	Approved
		Effective Date	5-Jan-2024
Document Number	PL-00052	Current Revision	5
Document Title	Clinical Validation of Freenome's Methylation Blood Test for the Early Detection...		
Document Category	Plan		

Age will be summarized using mean, standard deviation, median, interquartile range, minimum, and maximum values. For categorical variables (stratified age, race, ethnicity, etc.), the number and percentage of subjects in each category will be used.

8.4. Subgroup Analyses

Note: PREEMPT is not prospectively powered for subgroup analysis, nor is study alpha controlled for subgroup analysis. Reported analyses and p-values should be interpreted accordingly.

For subjects in the FAS, the condition prevalence (i.e. CRC, AA, Non-ACN) and clinical performance (unless otherwise noted, CRC sensitivity, AA sensitivity, and non-ACN specificity) of FMBT-CRC will be compared using Fisher-Freeman-Halton Exact tests for the following categorical variables (FDA 2017):

- Biological sex
- Race/ethnicity
- Categorical age brackets (note: for this analysis, a Cochrane-Armitage test for trend will be performed)
- Smoking status
- CS completion within 90 days vs. > 90 but \leq 120 days after blood collection
- For CRC, cancer stage
- For CRC, location (proximal, distal and rectal)
- For AA, sub-type (2.1-2.5)
- For AA, location (proximal, distal and rectal)
- For AA, index lesion size (\leq 5, 6-9, 10-19, 20-29, and \geq 30mm). (note: for this analysis, a Cochrane-Armitage test for trend will be performed)

The clinical performance of FMBT-CRC will also be analyzed via multivariate logistic regression (probability of a positive FMBT-CRC result as a function of listed variables) as follows:

This document contains confidential, proprietary information and may not be reproduced or disclosed in whole or in part without written authorization from Freenome Holdings, Inc

		Approval Status	Approved
		Effective Date	5-Jan-2024
Document Number	PL-00052	Current Revision	5
Document Title	Clinical Validation of Freenome's Methylation Blood Test for the Early Detection...		
Document Category	Plan		

- For NAA and AA (Categories 2-3), analysis of test positivity by index lesion size and location. The model will be repeated to also include age, biological sex, and race variables.
- For non-ACN, analysis of test positivity controlling for race, biological sex, and age.
- For CRC and AA (separately), analysis of test positivity, controlling for age, biological sex, race, index lesion size and lesion location.

Note: for multivariate logistic regression, Wald tests will be used to evaluate each factor for statistical significance, and age will be treated as a continuous factor.

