1.1. Background

CRC is the fourth most frequently diagnosed cancer and the second leading cause of cancer death in the United States. In 2022, an estimated 106,180 new cases of colon cancer and

This document contains confidential, proprietary information and may not be reproduced or disclosed in whole or in part without written authorization from Freenome Holdings, Inc

		Approval Status	Approved
		Effective Date	5-Jan-2024
Document Number	PL-00052	Current Revision	5
Document Title	Clinical Validation of Freenome's Methylation Blood Test for the Early Detection...		
Document Category	Plan		

44,850 new cases of rectal cancer were expected to occur in the United States, and it was estimated that 52,580 people would die from CRC (American Cancer Society, 2022). Screening for persons at average risk for CRC typically begins at age 50, and individuals at average risk have traditionally been defined as those aged \geq 50 years without personal history of inflammatory bowel disease (IBD), adenomas, or CRC; without a family history of CRC or AA; and without symptoms such as rectal bleeding (U.S. Preventive Services Task Force, 2016; Rex et al., 2017; Provenzale et al., 2018). Registry data from the National Cancer Institute's (NCI) Surveillance, Epidemiology, and End Results (SEER) program indicated an increased incidence of CRC in African Americans prior to age 50 years (Howlader et al., 2019), which led to the recommendation in 2005 that CRC screening in African Americans begin earlier, at age 45 (Rex et al., 2017). More recently, epidemiologic reports suggest that the incidence of CRC may be increasing in adults aged $<$ 50 years (Bailey et al., 2015; Meester et al., 2018; Peterse et al., 2018), leading the American Cancer Society in 2018 to recommend considering CRC screening in adults aged 45-49 years (Wolf et al., 2018). The U.S. Preventive Services Task Force also expanded the recommended ages for CRC screening to 45 to 75 years (Recommendation B) in 2021 (U.S. Preventive Services Task Force, 2021). Accordingly, private insurance plans have begun providing coverage for CRC screening in adults aged \geq 45 years in 2022 (Fight CRC, 2022).

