4.2. Inclusion and Exclusion Criteria

Inclusion Criteria

For enrollment to this study, subjects met all the following criteria:

This document contains confidential, proprietary information and may not be reproduced or disclosed in whole or in part without written authorization from Freenome Holdings, Inc

		Approval Status	Approved
		Effective Date	5-Jan-2024
Document Number	PL-00052	Current Revision	5
Document Title	Clinical Validation of Freenome's Methylation Blood Test for the Early Detection...		
Document Category	Plan		

1. 45-85 years of age (inclusive) within 30 days of enrollment (target ≥ 70% of subjects to be 65-85).
2. Willing to undergo a SOC CS within 90 days of blood collection.
3. Considered by a physician or healthcare provider to be “average-risk” for CRC.
4. Able and willing to provide blood samples per protocol.
5. Able to comprehend and willing to sign and date the written informed consent document(s).

Exclusion Criteria

Subjects were excluded from enrolling into the study if any of the following were met:

1. Family history
 - 1.1. At least one (1) first-degree relative diagnosed with CRC before the age of 60 (Note: First degree relatives include parents, siblings, and offspring).
 - 1.2. At least two (2) first-degree relatives diagnosed with CRC at any age.
 - 1.3. Known hereditary gastrointestinal cancer syndrome including but limited to the following:
 - Hereditary non-polyposis CRC syndrome or Lynch Syndrome
 - Familial adenomatous polyposis
 - Cowden's Syndrome
 - Juvenile Polyposis Syndrome
 - MUTYH-associated Polyposis
 - Peutz-Jeghers Syndrome
 - Serrated Polyposis Syndrome
2. Personal history
 - 2.1. CRC or colorectal adenoma
 - 2.2. History of malignancy (except for non-melanomatous skin cancer) at the time of enrollment, and for the 5 years preceding enrollment
 - 2.3. IBD, including chronic ulcerative colitis and Crohn's disease
 - 2.4. Total colonic resection
 - 2.5. Cystic fibrosis
 - 2.6. CS in the 9 years preceding enrollment with the exception of an incomplete colonoscopy, or for a poor or inadequate bowel prep
 - 2.7. Sigmoidoscopy or CT colonography in the 4 years preceding enrollment
 - 2.8. Stool DNA testing in the 2 years preceding enrollment
 - 2.9. Fecal occult blood testing or fecal immunochemical testing in the 6 months preceding enrollment

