8.5. Additional Analyses

1. Descriptive statistics for medical history, concomitant medication, adverse events, summary of blood test accessioning, processing, and findings, and summary of colonoscopy findings.
2. Diagnostic yield.
3. Report percentage of results with invalid tests.
4. Subject demographics and analysis of test performance (Sn, Sp, PPV, NPV, PLR and NLR) homogeneity by sites stratified by Science 37 and non-Science 37 sites, and US vs non-US sites.
5. Analysis of test performance (Sn, Sp, PPV, NPV, PLR and NLR) for the following age-based USPSTF (2021) Grade groups:
 - 5.1. USPSTF Grade "A" (50-75)
 - 5.2. USPSTF Grade "A+C" (50-85)
 - 5.3. USPSTF Grade "B+A" (45-75)
 - 5.4. USPSTF Grade "B+A+C" (45-85)
6. Comparison of age and sex distributions to US estimates.
7. NPV and PPV using U.S. IUP prevalence.

This document contains confidential, proprietary information and may not be reproduced or disclosed in whole or in part without written authorization from Freenome Holdings, Inc

		Approval Status	Approved
		Effective Date	5-Jan-2024
Document Number	PL-00052	Current Revision	5
Document Title	Clinical Validation of Freenome's Methylation Blood Test for the Early Detection...		
Document Category	Plan		

8. Direct rate standardization will be used to project the sensitivity (Sn_{ACN} , Sn_{CRC} , and Sn_{AA}) and specificity ($Sp_{non-ACN}$) of FMBT-CRC to the general population based on age brackets and biological sex. Standardization will be repeated, projecting for condition prevalence (based on age brackets and sex) to the general population, prior to projecting the sensitivity and specificity to the general population.
9. Number needed to screen per disease-positive finding (CRC, Stage I to III CRC, AA).

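### SAP 8.4 compares AA and CRC prevalence between sex, race/ethnicity and smoking groups without age adjustment; an age-adjusted AA comparison should sit beside the crude tests (minor)

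*SAP*

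**What the plan says.** SAP 8.4 has two targets: "For subjects in the FAS, the condition prevalence (i.e. CRC, AA, Non-ACN) and clinical performance" of the test. Both "will be compared using Fisher-Freeman-Halton Exact tests for the following categorical variables", a list that includes sex, race/ethnicity and smoking status. No stratification factor or covariate is named. Age appears only as a further item in that list: "Categorical age brackets (note: for this analysis, a Cochrane-Armitage test for trend will be performed".

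The section then adds regression, for one target only: "The clinical performance of FMBT-CRC will also be analyzed via multivariate logistic regression", with the outcome given as "probability of a positive FMBT-CRC result as a function of listed variables". All the models listed there analyze test positivity. None has CRC or AA as its outcome.

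SAP 8.5 item 8 does bring age to bear on prevalence: "Standardization will be repeated, projecting for condition prevalence (based on age brackets and sex) to the general population". This projects cohort results outward and compares no groups. Protocol 7.3.4 sets observed incidence against SEER expectation to judge representativeness, again without an age-adjusted comparison between groups.

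SAP 8.2 sets a nominal 0.05 level for tests outside the primary and secondary endpoints. SAP 8.4 opens with a caution that subgroup analyses are neither powered nor alpha-controlled. It does not mention confounding.

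**The concern.** Section 8.4 adjusts for age when it asks whether the test performs differently between groups, but not when it asks whether disease prevalence differs between them. If AA becomes more common with age, a younger group will show lower crude prevalence even when risk at a given age is the same. A younger group with truly higher risk at a given age may show no crude difference at all.

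AA is where this matters. At the SAP's own prevalence and FAS size there would be well over a thousand AA cases, enough for a crude test to pick up a difference due only to age mix. At stake is how a subgroup prevalence table is read. The co-primary criteria and the AA sensitivity endpoint are not involved.

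**Working it through.** **Inputs from the documents (SAP 7).** At least 56 CRC cases; CRC prevalence 0.30%; FAS 19,000; 20% unevaluable; enrollment 24,000; AA prevalence Beta(34.265, 436.699).

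**Reproducing the plan's figures.** 56 / 0.003 = 18,667, against 19,000 stated. 19,000 / 0.80 = 23,750, against 24,000 stated. Both agree within 2%. They only set the scale here; no figure in the plan is disputed.

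- AA prevalence: 34.265 / (34.265 + 436.699) = 7.28%, so 19,000 × 0.07276 = about 1,382 AA cases.
- CRC: 19,000 × 0.003 = 57 cases.

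**Assumptions not in the documents.** The five age brackets of SAP 8.3 hold 8, 7, 15, 45 and 25% of the cohort, so 70% are 65 or over, with midpoints 47, 52, 59.5, 69.5 and 80. AA log-odds are linear in age with odds ratio 1.28 per decade, calibrated to 7.28% overall. One subgroup is 15% of the FAS (2,850 against 16,150). Prevalence at a given age is the same in both groups.

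**Prevalence by age.** The bracket values are 4.40, 4.95, 5.89, 7.42 and 9.41%.

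- Under 65: (8 × 4.40 + 7 × 4.95 + 15 × 5.89) / 30 = 5.27%.
- 65 and over: (45 × 7.42 + 25 × 9.41) / 70 = 8.13%.

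**Crude comparison.** Let f be the subgroup's share aged 65 or over. The rest of the cohort then has (0.70 − 0.15f) / 0.85. The standard error of the difference is √[0.0728 × 0.9272 × (1/2,850 + 1/16,150)] = 0.528 percentage points. The rejection rate is Φ(−1.96 + d) + Φ(−1.96 − d), where d = difference / 0.528.

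| f | Rest aged 65+ | Subgroup AA | Rest AA | d | Crude test rejects |
|---|---|---|---|---|---|
| 65% | 70.9% | 7.13% | 7.30% | 0.32 | 6% |
| 60% | 71.8% | 6.99% | 7.33% | 0.64 | 10% |
| 50% | 73.5% | 6.70% | 7.38% | 1.27 | 25% |
| 40% | 75.3% | 6.42% | 7.43% | 1.91 | 48% |

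Simulation under the same inputs gives about 6%, 9%, 24% and 48%. An age-stratified Cochran-Mantel-Haenszel (CMH) test stays close to 5%. For odds ratios of 1.16 to 1.42 per decade and f from 60% to 40%, the crude rate runs from about 7% to about 75%.

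**A real difference hidden.** With a true subgroup odds ratio of 1.2 at a given age, simulated crude power is about 19% (f = 50%) or 6% (f = 40%). The stratified test has about 60-65%.

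**Different assumptions.** A separate simulation took half the cohort as 65 or over, an older-to-younger prevalence ratio of 1.5 to 3.0, a smaller group of 12% or 45%, and an age gap of 10 or 20 points. With no group effect given age, the crude prevalence ratio was 0.81 to 0.96. For AA the crude exact test rejected in 8-97% of runs and the CMH test in 3.5-6.0%. For CRC the ratio was biased equally, but the crude test rejected in only about 4-11%, because cases are few.

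**The case against.** **The crude test answers a legitimate question.** If a younger group has fewer AAs, its prevalence in the FAS really is lower, and a test that says so is correct. The rejections above are errors only against the null of equal prevalence at a given age, which 8.4 does not state. This stands. It is why the crude tests should stay, and why it would be wrong to infer that they are invalid.

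**Evidence that groups differ in age is thin.** A reader might infer an age difference by race from the SAP background, which cites a 2005 recommendation that "CRC screening in African Americans begin earlier, at age 45". The same section reports a 2018 recommendation to consider screening adults generally at 45-49 and a 2021 extension to ages 45 to 75. The FAS holds only subjects enrolled on or after April 5, 2021. The recruitment goal, "target ≥ 70% of subjects to be 65-85", applies to the whole cohort and implies no imbalance between groups. Nothing in the documents shows that sex or smoking groups differ in age. Confounding is a possibility here, not a finding.

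**The larger percentages need large gaps.** The 48% case sets 40% against 75% aged 65 or over. The calculation also compares two groups. If race/ethnicity had four categories and only one differed, a chi-square approximation gives about 7%, 16% and 32% for f of 60%, 50% and 40%. This too stands.

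**The section already carries a caution.** It does, but about power and alpha. Confounding is a bias, and a larger sample makes a difference due to age mix more likely to reach significance. The caution does not cover it.

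**Conclusion.** The gap is real and small. No between-group prevalence comparison in the SAP is age-adjusted, although the section adjusts test positivity for age. For AA, the crude result could carry an age difference or conceal a real one. How much depends on each group's age mix and on the age gradient, and the documents give neither. The figures above show direction and plausible size under stated assumptions; they do not predict what this study will find.

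Three stronger readings are not supported. The SAP does not ignore age in prevalence altogether, because 8.5 item 8 standardizes by age bracket and sex. Nothing in it says that a crude prevalence p-value will be reported as a finding on disease burden. CRC comparisons are not materially at risk of false rejection with about 57 cases. No primary or secondary criterion, sample size or success rule is touched. This is a minor improvement of optional weight.

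**What to change.** In SAP 8.4, keep the crude exact tests and label them a description of observed prevalence. Beside them, for each of sex, race/ethnicity and smoking status, add an age-adjusted comparison of AA prevalence: either a logistic model with the group variable and continuous age, or a CMH test stratified by the SAP 8.3 age brackets. For CRC, add at most a group-plus-age model or an age-stratified exact analysis; the case count does not justify a larger one. State that the adjusted result is the basis for any claim that groups differ in prevalence beyond their age mix.

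The cost is one or two sentences and a few short models on variables already collected. Naming them before results are seen also avoids choosing covariates afterwards.

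### The adjusted CRC model in SAP 8.4 fits at least six slopes to about 8 to 11 expected false negatives with Wald tests; Firth penalized likelihood with a race-pooling rule is better at almost no cost

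*SAP*

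**What the plan says.** SAP 8.4 lists several multivariable logistic models for the probability of a positive test. One is fitted within cancers and, separately, within advanced adenomas: "For CRC and AA (separately), analysis of test positivity, controlling for age, biological sex, race, index lesion size and lesion location". For all these models, "Wald tests will be used to evaluate each factor for statistical significance, and age will be treated as a continuous factor". The section does not state how race or lesion size is coded, and it gives no rule for sparse categories or for a model without a finite solution.

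The same section plans unadjusted comparisons of prevalence and test performance, which "will be compared using Fisher-Freeman-Halton Exact tests for the following categorical variables". These cover sex, race/ethnicity, smoking, colonoscopy timing and, within CRC, stage and location ("For CRC, location (proximal, distal and rectal"). Age gets a trend test. An unadjusted lesion-size comparison is listed for AA only. The section also states that subgroup analyses are neither powered nor alpha-controlled, and adds: "Reported analyses and p-values should be interpreted accordingly".

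On numbers, SAP 7 says: "The study should include a minimum of 56 evaluable CRC cases". SAP 7.1 assumes at least 85% sensitivity and, for 56 cases, "then at least 44 need to be positive by the FMBT-CRC".

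**The concern.** In a logistic model the rarer outcome limits how many slopes the data can support. Among cancers the rarer outcome is a false negative, and a test that performs as planned produces few of them. Two problems follow.

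- **Separation.** If some combination of covariates splits the positives from the negatives, even partly, at least one maximum-likelihood estimate runs to infinity. Its standard error grows faster than the estimate, so the Wald test says almost nothing. A location or race group with no false negatives is enough.
- **Bias.** Where estimates are finite, maximum likelihood with so few events overstates effects.

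At stake are the adjusted CRC results in the study report. In particular, this model is the only planned analysis of lesion size within CRC.

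**Working it through.** **1. The plan's own figure.** For 44/56 the Wilson lower bound is [p + z²/2n − z√(p(1−p)/n + z²/4n²)] / (1 + z²/n), with p = 0.7857, n = 56 and z = 1.96. This is (0.7857 + 0.0343 − 0.1128) / 1.0686 = 66.2%, as SAP 7.1 states. 43/56 gives 64.2%, so 44 is the right critical value. Exact power at 85% sensitivity is 93.2%, consistent with the stated 90% or more.

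**2. Slopes.** Age 1, sex 1, race at least 1, lesion size at least 1, location 2 (three levels): at least 6. Four race groups give 8.

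**3. Expected false negatives.**
- Planned minimum: 56 × 0.15 = 8.4.
- Upper case: SAP 7 says "the prevalence of CRC is estimated to follow a beta distribution with parameters 3.264 and 816.77". The mean is 3.264/(3.264 + 816.77) = 0.398%. On the SAP's 19,000 evaluable subjects this gives 75.6 cancers, and 75.6 × 0.15 = 11.3.
- Most compatible with success at n=56: 56 − 44 = 12.
- Per slope: 8.4/6 = 1.4 and 11.3/6 = 1.9.

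**4. How often separation occurs.** There were 2,000 simulated data sets per setting, checked by linear programming, with no true effects and 85% sensitivity. Assumed covariates: age and size standard normal, sex 50/50, location 40/35/25.

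| Race split | n=56 | n=76 |
|---|---|---|
| 70/30 | 24.9% | 10.2% |
| 85/15 | 39.8% | 23.3% |
| 70/20/10 | 61.3% | 43.0% |
| 75/13/6/6 | 90.8% | 82.9% |

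With 12 expected false negatives at n=56 (78.6% sensitivity), the rates are 9.3%, 39.0% and 81.5% for two, three and four race groups. A run with other shares (location 40/30/30, race minority 25% or 10%, a true size effect) gave 28% to 52% at n=56 with six slopes.

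**5. Which slopes are affected.** With no true effect, the size slope was non-finite in at most 1% of data sets at n=56 and in none at n=76. With a true size log odds ratio of 1.0 per SD, it was non-finite in 1.4-3.0% and 0.2-0.4%. Separation therefore sits almost entirely in the race and location slopes.

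**6. Size slope where finite (true value 1.0, two race groups).**
- n=56: standard mean 1.47, median 1.24; Firth mean 1.03 on the same data sets. Root mean square error 1.15 against 0.51.
- n=76: standard mean 1.23 to 1.25; Firth 1.00. Root mean square error 0.66 against 0.45.
- Rejection at the 5% level, Wald against Firth: 55% and 60% (n=56), 75% and 74% (n=76). Under the null: 4.3-5.0% and 4.7-4.9%.

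**7. Location tests (5% level).**

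| True sensitivity by location | n | Wald | Firth | Planned exact test |
|---|---|---|---|---|
| 69/97/90% | 56 | 10% | 53% | 62% |
| 69/97/90% | 76 | 29% | 74% | 79% |
| 75/93/90% | 56 | 6% | 21% | 28% |
| 75/93/90% | 76 | 16% | 35% | 41% |

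Null rejection for location was 1.2-1.5% (Wald) and 3.1-3.3% (Firth).

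**The case against.** The strongest case is that little is lost. SAP 8.4 already disclaims power and alpha control. Sex, race, location and age in CRC each have an unadjusted exact or trend test, and for location the exact test finds an effect more often than either adjusted test. For lesion size, the one question that only this model addresses, the Wald and Firth tests perform alike. The only output the SAP names for these models is the test, not an adjusted odds ratio or its interval. The Wald test errs toward too few rejections, so it creates no false claims. The figure of 56 is a minimum, and SAP 4 describes the study as overpowered. Protocol 7 lets changes of method be justified in the study report.

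Most of this stands and limits the point to a refinement. Three things remain. The disclaimer concerns power and alpha, and does not warn of infinite or biased estimates. The documents give no realized CRC count that would show the problem has gone away. A remedy chosen after the model has failed is chosen with the data in view.

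A reader might infer from the separation rates that the lesion-size analysis is lost, or from the location figures that differences by location will be missed. Neither follows: the size slope is nearly always finite, and SAP 8.4 plans the exact location test separately. Nor does the mean of 1.47 describe a typical data set, because a few near-separated ones pull it up; the median is about 1.24.

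**Conclusion.** The concern holds in a limited form. For the adjusted CRC model, standard maximum likelihood with Wald tests is a poor match for about 8 to 11 false negatives and six or more slopes. Non-finite estimates are likely enough to plan for, and race grouping is the main driver: at n=56 the rate runs from about 25% with two balanced groups to 91% with four. The harm is confined to adjusted race and location estimates that may be unusable and to a size estimate that is overstated. The primary and secondary endpoints, the acceptance criteria and the sample size are untouched. The AA model, planned on 1,929 cases with about 270 positives (1,929 × 0.14), does not share the problem.

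The false-negative counts follow from the SAP's own inputs. The separation rates, bias and rejection rates rest on assumed covariate shares and effect sizes, since the documents give none. More cancers or lower sensitivity would reduce the rates.

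**What to change.** In SAP 8.4, for the CRC model only:

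- Fit by Firth penalized likelihood, test each factor with a penalized likelihood-ratio test, and report profile-likelihood confidence intervals.
- Pool sparse race categories by a rule fixed before unblinding. Firth does not cure an empty category, which occurred in 3-7% of simulated data sets with four race groups.

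Leave the other logistic models, the exact and trend tests, and the coding of lesion size as they are.

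The cost is two or three sentences in the SAP, with no new data. The downsides are slight shrinkage of estimates and fitted probabilities pulled toward 0.5, so the model should not be used to estimate sensitivity. Power for moderate effects stays low.
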